The measurements of cervical length will be performed by the perinatology team in two different periods of pregnancy (11-14 and 18-22 weeks of gestation) in the singleton pregnancies. Firstly, the vaginal swabs of women who accept to participate in the study will be collected at 11-14th weeks of gestation just before the measurement of cervical length. Also, the vaginal swabs through the aforementioned procedure will be collected at

18-22 weeks of gestation. Micronized progesterone will be started in women with a cervical length equal or less than 25 mm (smaller than 3rd percentile) at 18-22 weeks of gestation. The medication (progesterone 200mg) will be administered intravaginally every night before bedtime and will continue until 36th gestational week unless the patient gives birth. Measurement of cervical length will be repeated transvaginally at 28th and 32nd gestational weeks, and samples will be taken with vaginal swab before these measurements. In order to evaluate the presence of placental mycobiota and microbiota after birth, 1 cm x 1 cm x 1 cm of tissue sample from placenta that is 3 cm lateral of the cord insertion will be taken under sterile conditions. In order to evaluate the amniotic compartment, buccal mucosal swabs will be taken from the neonates immediately after birth. All samples taken during pregnancy follow-up and after delivery will be delivered to our Research Laboratory immediately and will be kept and stored in -80 degrees cabinet until the evaluation.

Study population

The study will plan to take 2 years for recruitment of patients. The enrollment of 60 participants with singleton pregnancies who have cervical length of 25 mm or less would give the study a power of 85% to show a treatment effect at a two-sided alpha level of 5%. The risk of preterm birth in a pregnant with a cervical length of 25 mm or less is 30%. The rate of preterm birth is 12% in the whole population. Thirty-two women who delivered at term with cervical length of longer than 25 mm will be in the control group. For the recruitment of study group, 1429 women with singleton pregnancies will need to be screened.

The patients will be included in the study group;

- 1) Pregnant women with cervical length of 25mm or less (n=60)

A) Of 60 patients, 30% will be expected to give a birth before 37 gestational weeks (n=18)

B) Of 60 patients, almost 70% will be expected to give a birth at term (n=42)

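### The only power figure, 85% for a treatment effect in 60 short-cervix women, belongs to no comparison the protocol states and says nothing about its preterm-versus-term microbiota hypothesis

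*Protocol*

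**What the plan says.** Under Study population, enrolling 60 women with a cervix of 25 mm or less "would give the study a power of 85% to show a treatment effect at a two-sided alpha level of 5" per cent. No endpoint, comparator or effect size is attached to this. The next two sentences give birth rates: "The risk of preterm birth in a pregnant with a cervical length of 25 mm or less is 30" per cent, and "The rate of preterm birth is 12% in the whole population".

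The same section lists the study group as "Pregnant women with cervical length of 25mm or less (n=60"), split by expected outcome: "Of 60 patients, 30% will be expected to give a birth before 37 gestational weeks (n=18") and "almost 70% will be expected to give a birth at term (n=42"). The control group is 32 women with a cervix longer than 25 mm who deliver at term. To reach these numbers, "1429 women with singleton pregnancies will need to be screened".

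On treatment, Study Procedure says "Micronized progesterone will be started in women with a cervical length equal or less than 25 mm". Vaginal swabs are taken at 11-14 and 18-22 weeks and again at 28 and 32 weeks.

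The Introduction gives the hypothesis: among short-cervix women receiving progesterone, microbiota and mycobiota differ between those who deliver preterm and those who deliver at term. It also defines the study group differently, as women with both a short cervix and a preterm birth.

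**The concern.** A power figure means something only for a named contrast and a named effect. Here the named effect is a treatment effect, and the protocol sets up no comparison that estimates one. There is no untreated short-cervix group. The controls differ from the treated women in cervical length and are chosen on the outcome. The serial swabs would allow a comparison of samples before and during progesterone, but the protocol does not state one, and gestational age would confound it.

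The hypothesis it does state concerns microbiota by birth outcome. The 85% is not linked to that, and 60 is not the size of either group in that contrast. The two study-group definitions make it harder still to tell what the figure refers to: 18 against 42, 18 against 32, 60 against 32, or something else.

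At stake is the study's only statement of adequacy. A reader, funder or ethics committee would take 85% as assurance about the main question, and it gives none.

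**Working it through.** **Inputs from the protocol.** Power 85%, two-sided 5%, 60 short-cervix women, expected split 18 preterm and 42 term, 32 controls, 1429 screened, preterm rates 30% and 12%. No microbiota effect size, SD or prevalence is given.

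**1. Can the 85% be reproduced?** The only candidate inputs are the two birth rates, whose difference is 0.30 - 0.12 = 0.18.

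*60 women against a fixed 12%.*
- Variance under the alternative: SE = sqrt(0.30 × 0.70 / 60) = 0.0592. Power = Φ(0.18/0.0592 - 1.96) = Φ(1.08) = 86%.
- Variance under the null for the critical value: SE0 = sqrt(0.12 × 0.88 / 60) = 0.0420. Power = Φ((0.18 - 1.96 × 0.0420)/0.0592) = 95%.
- Exact binomial: reject at 13 or more events (upper-tail probability 0.024 at 12%). Power at 30% is 94%.

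*60 women against the other 1429 - 60 = 1369 screened.*
- At 12% in the remainder: 85% with unpooled variance, 94% pooled.
- If 12% is the overall rate, the remainder rate is (0.12 × 1429 - 18)/1369 = 11.2%: 88% unpooled, 96% pooled.

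*60 against 32, at 30% and 12%.* 49% pooled, 59% unpooled. This comparison is in any case empty, because the controls have no preterm births by definition.

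So 85 to 86% appears only for a comparison of birth rates with one choice of variance. The text does not say that this was the calculation.

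**2. What the design offers for the stated hypothesis.** For illustration, take one continuous microbiota measure at one time point, a two-sample t test at two-sided 5%, and no multiplicity adjustment. For a standardised difference d the noncentrality is d × sqrt(n1 n2/(n1 + n2)). As a first approximation, d at 85% power is (1.960 + 1.036) × sqrt(1/n1 + 1/n2). For 18 against 42 this is 2.996 × 0.2817 = 0.844, and the noncentral t gives 0.858.

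| Contrast | d for 85% power | Power at 0.5 SD | Power at 0.8 SD |
|---|---|---|---|
| 18 preterm vs 42 term, all short cervix | 0.86 | 42% | 80% |
| 18 preterm vs 32 controls | 0.90 | 38% | 76% |
| 18 preterm vs all 74 term (42 + 32) | 0.80 | 47% | 85% |
| 60 short cervix vs 32 controls | 0.66 | 62% | 95% |

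The 0.5 and 0.8 SD columns are assumed benchmarks shown as a range. The last row mixes preterm and term births in one arm, so it does not test the hypothesis.

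**3. Uncertainty in the 18.** With 60 women and a true risk of 30%, the 2.5% and 97.5% binomial quantiles are 11 and 25 preterm births. For 11 against 49, d at 85% power is 1.02. For 25 against 35 it is 0.80.

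**The case against.** The best defence is that the 30% and 12% rates follow directly after the power sentence and, with 60 women, can give 85 to 86%. On that reading the authors did a sound birth-rate calculation and mislabelled it. This is plausible but unconfirmed, since other standard variance choices give 94 to 95%. It also does not rescue the statement: the label would still be wrong, and the figure would still not concern microbiota.

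A second defence is that the test, the diversity measure and the multiplicity rule may properly sit in a statistical analysis plan that is not shown. That stands, and their absence is not counted here. The fault is in what the protocol itself asserts: power for an effect that its stated comparisons do not estimate.

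Two further points have force. Power at 0.5 SD depends on a benchmark the protocol does not supply, and at 0.8 SD the picture is much better, so the detectable differences are the safer summary. Also, only 18 against 42 stays within short-cervix women. Against the 32 controls, cervical length and progesterone differ as well, and the protocol never defines the pooled 74 as a comparison group.

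**Conclusion.** The concern holds. The 85% is attached to a treatment effect that no stated comparison in the protocol estimates, and it gives no information about the microbiota hypothesis. The figure is not arithmetically impossible: it may be a comparison of preterm-birth rates, but the text does not say so.

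For the preterm-versus-term contrast within short-cervix women, 85% power needs a difference of about 0.86 SD, or between 1.02 and 0.80 SD over the plausible range of 11 to 25 preterm births. This rests on one continuous measure at one time point, a t test, no multiplicity adjustment, and the protocol's own 30% risk. Testing many taxa, or bacteria and fungi together, with multiplicity control would raise the detectable difference.

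This should be fixed because it is the only sample-size justification. It does not make the data unusable.

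**What to change.** - Delete the claim of 85% power for a treatment effect, or say what it refers to. If the 30% against 12% calculation was meant, call it a comparison of preterm-birth rates and name the comparator and test. If a change from before to during progesterone was meant, state that comparison and that it has no concurrent untreated group.
- In either case, add a precision statement for the Introduction's hypothesis. For example: with 18 preterm births expected among 60 short-cervix women, a two-sided 5% t test of one continuous microbiota measure against the 42 term births has 85% power for a difference of about 0.86 SD (1.02 to 0.80 SD for 11 to 25 preterm births), before any multiplicity adjustment. If the 32 controls are also used, give 0.90 SD and note that cervical length and progesterone differ too.
- Reconcile the study-group definitions in the Introduction and Study population, so that the contrast is unambiguous.
- Say whether the 30% is the risk under progesterone, because the expected 18 depends on it.

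The cost is protocol wording, with no extra patients or samples. The stated figure becomes less favourable, and the authors must commit to a contrast.
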